**Clinical Laboratory Tests**

Abbreviations: Ab = antibody; DNA = deoxyribonucleic acid; HBV = hepatitis B virus; HCV = hepatitis C virus; IgA = immunoglobulin A; RNA = ribonucleic acid; RBC = red blood cells; SGOT = serum glutamic oxaloacetic transaminase; SGPT = serum glutamic pyruvic transaminase; T4 = thyroxine; WBC = white blood cells.

- a Unscheduled blood chemistry, hematology, and urinalysis panels may be performed at the discretion of the investigator.
- b Cockcroft-Gault calculation is used for the calculated creatinine clearance.
- c For the fasting lipid profile, patients are not to eat or drink anything except water for 12 hours prior to test. Fasting is not required for the Screening Visit.
- d Serum pregnancy test for all women <60 years of age who are still of childbearing potential at Visit 1; after Visit 1, urine pregnancy test performed locally for women of childbearing potential.
- e Women  $\geq 40$  and <60 years of age who have had a cessation of menses for  $\geq 12$  months will have an FSH test confirming nonchildbearing potential ( $\geq 40$  mIU/mL).
- f Test required at Visit 1 to determine eligibility of patient for the study.
- g HBV DNA testing will be done in those patients who HBcAb+ at any time
- h See exclusion criteria (Section 5.2) specific to Hepatitis C antibody. A confirmatory test for HCV will be performed if the patient is positive for HCV antibody.
- i In countries where the QuantiFERON®-TB Gold test or T-SPOT® is available, either test may be used instead of the PPD TB test. The QuantiFERON-TB Gold test may be performed locally or centrally; the T-SPOT must be performed locally.

---

## Appendix 4. Hepatic Monitoring Tests for Treatment-Emergent Abnormality

---

Selected tests may be obtained in the event of a treatment-emergent hepatic abnormality and may be required in follow-up with patients in consultation with the Lilly, or its designee, clinical research physician.

### Hepatic Monitoring Tests

---

#### Hepatic Hematologya

Hemoglobin  
Hematocrit  
RBC  
WBC  
Neutrophils, segmented  
Lymphocytes  
Monocytes  
Eosinophils  
Basophils  
Platelets

#### Hepatic Chemistrya

Total bilirubin  
Direct bilirubin  
Alkaline phosphatase  
ALT  
AST  
GGT

#### CPK

#### Haptoglobina

#### Hepatic Coagulationa

Prothrombin Time  
Prothrombin Time, INR

#### Hepatic Serologiesa,b

Hepatitis A antibody, total  
Hepatitis A antibody, IgM  
Hepatitis B surface antigen  
Hepatitis B surface antibody  
Hepatitis B Core antibody  
Hepatitis C antibody  
Hepatitis E antibody, IgG  
Hepatitis E antibody, IgM

#### Anti-nuclear antibodya

#### Alkaline Phosphatase Isoenzymesa

#### Anti-smooth muscle antibody (or anti-actin antibody)a

---

Abbreviations: ALT = alanine aminotransferase; AST = aspartate aminotransferase; CPK = creatinine phosphokinase; GGT = gamma-glutamyl transferase; Ig = immunoglobulin; INR = international normalised ratio; RBC = red blood cells; WBC = white blood cells.

a Assayed by Lilly-designated or local laboratory.

b Reflex/confirmation dependent on regulatory requirements and/or testing availability.

---

## Appendix 5. Spondyloarthritis Features

---

To be included in Study RHBX, patients must fulfill the ASAS criteria for nonrad-axSpA either by:

(a) presence of sacroiliitis on MRI (according to ASAS/OMERACT criteria and based on central reading) (Rudwaleit et al. 2009d) and have at least 1 SpA feature from the bulleted list below.

**OR**

(b) being HLA-B27 positive and have at least 2 additional SpA features from the bulleted list below.

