Although the exact etiology is unknown, genetic factors and several loci are likely to be involved in susceptibility to axSpA (Reveille 2011). There is a strong association with the major histocompatibility complex, HLA-B27. The risk of developing axSpA is as high as about 5% in HLA-B27 positive individuals. Similar findings are obtained in the HLA-B27-positive relatives of such patients (Braun and Sieper 2007). Up to approximately 70% of patients with nonrad-axSpA have been reported to be positive for HLA-B27 (Gulfe et al. 2014). Most of the other known genetic susceptibility comes from genes involved in cytokine production, specifically including genes in the T helper (Th)17 pathway (Maksymowych 2010; Reveille 2011).

Current standard of care for nonrad-axSpA includes regular exercise, physical therapy, and nonsteroidal anti-inflammatory drugs (NSAIDs). TNF inhibitors have also demonstrated efficacy in nonrad-axSpA; however, they are not yet approved globally for this indication (Braun et al. 2011; Robinson et al. 2014; Ward et al. 2015), and approximately 40% of patients only obtain a partial response on TNF inhibitors (Sieper et al. 2012, 2013; Landewé et al. 2012; Dougados et al. 2014). Corticosteroid injections may also be of some benefit. Though NSAIDs are the first line of drug treatment for axSpA, they are not effective or well tolerated in all patients (Braun and Sieper 2009). In contrast to patients with RA, patients with axSpA do not respond well to conventional disease-modifying antirheumatic drugs (cDMARDs) or systemic corticosteroids (Braun and Sieper 2009; Haibel and Specker 2009).

TNF inhibitors have demonstrated efficacy across the axSpA spectrum and may be prescribed for nonrad-axSpA when NSAID treatment has failed or cannot be tolerated (Braun et al. 2014) and where regulatory approval has been obtained for this population. To date few treatment options are globally available for nonrad-axSpA (van der Heijde et al. 2006; Heiberg et al. 2008; Inman et al. 2008; Glinborg et al. 2010).

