#### Type of Patient and Disease Characteristics

- [1] Presence of sacroiliitis on MRI (according to ASAS/OMERACT criteria and based on central reading) (Rudwaleit et al. 2009d) and have at least 1 SpA feature  
OR  
Are positive for HLA-B27 and have at least 2 additional SpA features, according to the ASAS criteria (Sieper et al. 2009; Rudwaleit et al. 2009a); SpA features listed in [Appendix 5](#).
- [2] Patients have a history of back pain  $\geq 3$  months with age at onset  $< 45$  years.
- [3] Have active nonrad-axSpA defined as BASDAI  $\geq 4$  and total back pain  $\geq 4$  on a NRS at screening and baseline (Sieper et al. 2009)
- [4] Patients have objective signs of inflammation by presence of sacroiliitis on MRI (as defined by ASAS/OMERACT) or presence of elevated CRP (defined as CRP  $> 5.00$  mg/L).
- [5] Must have had an inadequate response, as determined by the investigator, to 2 or more NSAIDs at the therapeutic dose range for a total duration of at least 4 weeks OR have a history of intolerance to NSAIDs

- [6] Patients must have a history of prior therapy for axSpA of at least 12 weeks prior to screening. Examples of prior therapy may include but are not limited to physical therapy and NSAID treatment.

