## 6.2. Method of Treatment Assignment

Patients who meet all criteria for enrollment will be randomized to double-blind treatment at Week 0 (Visit 2). Assignment to treatment groups will be determined by a computer-generated random sequence using an IWRS. The IWRS will be used to assign double-blind investigational product to each patient. Site personnel will confirm that they have located the correct

investigational product package by entering a confirmation number found on the package into the IWRS.

To achieve between-group comparability, the randomization will be stratified by country and screening MRI/CRP status (positive MRI and elevated CRP; positive MRI and nonelevated CRP; negative MRI and elevated CRP). Elevated CRP is defined as  $>5.00$  mg/L.

Target enrollment will be a minimum of approximately 20% for each of the MRI/CRP strata. Once a specific stratum is fully enrolled, the sponsor may stop further enrollment of patients fitting the criteria of that stratum.

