#### **6.15. Subgroup Analyses**

##### **6.15.1. Efficacy Subgroup Analyses**

Subgroup analysis will be conducted for the primary endpoints of proportion of patients achieving an ASAS40 response at Weeks 16 and 52 (NRI) using the ITT Population for the Period 2. The proportion of patients achieving ASDAS <2.1 (NRI) at Weeks 16 and 52, will also be conducted.

For ASAS40, ASDAS <2.1, a logistic regression analysis with treatment, subgroup, and treatment-by-subgroup interaction as factors will be used. The treatment-by-subgroup interaction will be tested at the 10% significance level. Treatment group differences will be evaluated within each subgroup using the Fisher's exact test, regardless of whether the interaction is statistically significant. If any group within the subgroup (for example, yes, no) is <10% of the total population, only descriptive statistics will be provided for that subgroup (that is, no inferential testing).

Forest plots may be created to illustrate the treatment differences with 95% CIs between each of the ixekizumab treatment groups and placebo group, by each subgroup category.

The following subgroups will be analyzed:

- Patient Demographics Subgroups:
  - Sex
  - Age category: <40 years, ≥40 years
  - Age category: <50 years, ≥50 years
  - Age category: <65 years, ≥65 years
  - Weight: <70 kg, ≥70 kg
  - BMI: underweight (<18.5 kg/m^2); normal (≥18.5 and <25 kg/m^2); overweight (≥25 and <30 kg/m^2); obese (≥30 and <40 kg/m^2); or extreme obese (≥40 kg/m^2)
  - Ethnicity: Hispanic/Latino, Non-Hispanic/Non-Latino

- Race: American Indian/Alaska Native, Asian, Black/African American, Native Hawaiian or other Pacific Islander, White, or Multiple
- Geographic Region Subgroups:
  - Geographic region: Europe, non-Europe
  - Geographic region: America, Asia, Europe
  - Geographic region: North America (US, including Puerto Rico if any, Canada) or Rest of the World
  - Geographic region: US (including Puerto Rico if any), non-US
  - Geographic region: South America (Argentina, Brazil and Mexico), Rest of the World (non-South America)
- Baseline Severity of Disease Subgroups:
  - Baseline CRP categories:
    - $\leq 3.00$  mg/L or  $> 3.00$  mg/L
    - $\leq 5.00$  mg/L or  $> 5.00$  mg/L
    - $\leq 10.00$  mg/L or  $> 10.00$  mg/L
    - $\leq 15.00$  mg/L or  $> 15.00$  mg/L
  - Baseline MRI status:
    - SPARCC SIJ score  $\geq 2$  or  $< 2$
  - Screening MRI/CRP status:

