    - positive MRI and elevated CRP
    - positive MRI and nonelevated CRP
    - negative MRI and elevated CRP

*Note: Positive MRI is defined by Assessment of SpondyloArthritis international Society/ Outcome Measures in Rheumatology Clinical Trials (ASAS/OMERACT) criteria and elevated CRP is defined as  $> 5.00$  mg/L.*
  - Baseline BASDAI:
    - $4 \leq \text{BASDAI} < 6$  or  $\text{BASDAI} \geq 6$
  - Baseline ASDAS:
    - $\text{ASDAS} \leq 3.5$  or  $\text{ASDAS} > 3.5$
- Other Patient Characteristics Subgroups:
  - Duration of symptom since AxSpA onset category:  $< 10$  years or  $\geq 10$  years
  - Duration of symptom since AxSpA onset category:  $< 5$  years or  $\geq 5$  years
  - Duration of symptom since AxSpA onset category:  $< 3$  years or  $\geq 3$  years
  - HLA-B27 status: positive or negative
  - Smoking status: current or former/never
  - Concomitant cDMARDs (methotrexate, sulfasalazine, hydroxychloroquine) at baseline: yes or no
  - History of arthritis: yes or no
  - History of uveitis: yes or no
  - History of dactylitis: yes or no
  - History of psoriasis: yes or no
  - History of enthesitis: yes or no
  - History of inflammatory bowel disease: yes or no

- History of extra-axial involvement: yes or no
- Baseline analgesics use: yes or no

Additional subgroup analyses on efficacy may be performed as deemed appropriate and necessary.

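### Every eligible HLA-B27-negative patient is screening-MRI-positive, so the HLA-B27 subgroup comparison in SAP 6.15.1 absorbs part of any difference in ixekizumab effect between MRI/CRP strata

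*Protocol*

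**What the plan says.** **Entry.** Inclusion criterion [1] and Protocol Appendix 5 give two routes. One is sacroiliitis on MRI, by central ASAS/OMERACT reading, with at least one SpA feature. The other reads "Are positive for HLA-B27 and have at least 2 additional SpA features, according to the ASAS criteria" in criterion [1] and "b) being HLA-B27 positive and have at least 2 additional SpA features from the bulleted list below" in Appendix 5. Criterion [4] adds: "Patients have objective signs of inflammation by presence of sacroiliitis on MRI (as defined by ASAS/OMERACT) or presence of elevated CRP".

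**Strata.** Randomization is stratified by country and screening MRI/CRP status, with three MRI/CRP levels. Protocol 6.2 states: "Target enrollment will be a minimum of approximately 20% for each of the MRI/CRP strata".

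**HLA-B27 prevalence.** The only figure is in the background (Protocol 2.1): "Up to approximately 70% of patients with nonrad-axSpA have been reported to be positive for HLA-B27". It is not a forecast for this trial.

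**Subgroup analysis.** SAP 6.15.1 lists "HLA-B27 status: positive or negative" among the efficacy subgroups for ASAS40 and ASDAS <2.1 at Weeks 16 and 52. For these endpoints "a logistic regression analysis with treatment, subgroup, and treatment-by-subgroup interaction as factors will be used". The interaction is tested at 10%, with Fisher's exact test within each subgroup level. Inference is dropped only for levels below 10% of the population. Protocol 9.7.2 gives the same model for ASAS40. Screening MRI/CRP status is a separate subgroup in the same list.

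**The concern.** A subgroup comparison is usually read as showing whether the named factor changes the treatment effect. Here the two HLA-B27 groups differ in MRI status by construction: one contains no MRI-negative patients and the other contains all of them. This is not chance imbalance, so neither randomization nor a larger sample removes it.

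If ixekizumab works less well (or better) in the negative-MRI/elevated-CRP stratum, the HLA-B27-positive estimate is pulled down (or up) and the HLA-B27-negative estimate is not. The interaction p-value, the within-group tests and any forest plot would then show an HLA-B27 difference even if HLA-B27 played no part. If both factors matter, they could also mask each other.

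**Working it through.** **Which patients can enter.** Applying criteria [1] and [4] to the eight combinations, assuming the required SpA features are present:

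| HLA-B27 | MRI | CRP | Eligible |
|---|---|---|---|
| − | − | normal | no ([1], [4]) |
| − | − | elevated | no ([1]) |
| − | + | normal | yes |
| − | + | elevated | yes |
| + | − | normal | no ([4]) |
| + | − | elevated | yes |
| + | + | normal | yes |
| + | + | elevated | yes |

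No eligible patient is both HLA-B27 negative and MRI negative. This step needs no assumption.

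**The plan's own figure.** Neither document gives an operating characteristic for the HLA-B27 test. The planning rates used below (46% v 18%, 100 per arm, two-sided Fisher's exact test at 0.05) give 98.8% power, against the stated approximate 98%.

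**Size of the shift.** Let f be the MRI-negative share of the trial, h the HLA-B27-positive share, and e+ and e− the risk differences in MRI-positive and MRI-negative patients. If HLA-B27 has no effect of its own:

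- HLA-B27 negative: e+
- HLA-B27 positive: (1 − f/h)·e+ + (f/h)·e−
- apparent gap: (f/h)·(e+ − e−)

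Inputs from the documents: f of at least about 20%, h up to about 70%, placebo 18%, average ixekizumab response 46%, 100 per arm. Assumed: h = 70%, f = 30% and 40% as larger shares, e+ − e− of 15 or 25 points, and placebo 18% in every stratum.

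Worked example, f = 40% and a 25-point gap:

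- MRI-positive response on ixekizumab: 46 + 0.40 × 25 = 56%
- MRI-negative: 56 − 25 = 31%
- HLA-B27 positive: 56 − (0.40/0.70) × 25 = 41.7%
- Odds ratio, HLA-B27 negative: (0.56/0.44)/(0.18/0.82) = 5.80
- Odds ratio, HLA-B27 positive: (0.417/0.583)/(0.18/0.82) = 3.26

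The other rows follow in the same way. The last column is the simulated rejection rate at 0.10 for the planned interaction (Q2W v placebo, 1 df, Wald-type test).

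| f | Assumed gap (points) | MRI− among HLA-B27+ (f/h) | Apparent gap (points) | Odds ratio, HLA-B27− v + | Rejects |
|---|---|---|---|---|---|
| 20% | 15 | 29% | 4.3 | 4.38 v 3.68 | about 9% |
| 20% | 25 | 29% | 7.1 | 4.74 v 3.56 | about 11% |
| 30% | 15 | 43% | 6.4 | 4.65 v 3.59 | 10-11% |
| 30% | 25 | 43% | 10.7 | 5.24 v 3.41 | about 14% |
| 40% | 15 | 57% | 8.6 | 4.94 v 3.50 | about 12% |
| 40% | 25 | 57% | 14.3 | 5.80 v 3.26 | about 18% |

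With no MRI effect modification the same test rejects in about 9% of trials; it is slightly conservative. Restricted to MRI-positive patients it also rejects in about 9% in every row, so the excess comes from MRI status.

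**The case against.** **The subgroup list is a set of one-factor consistency checks.** The SAP does not claim to estimate an HLA-B27 effect independent of MRI, and a result for HLA-B27-positive and -negative patients as enrolled is a legitimate description. This stands. A reader might infer that the planned analysis is useless or that the plan draws a causal conclusion; the documents support neither. What remains is that the plan carries no caution about an overlap fixed by its own eligibility rules.

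**The MRI/CRP subgroup is shown separately.** It would reveal a real MRI/CRP difference, which helps. It does not show whether HLA-B27 matters once MRI status is fixed.

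**Models adjust for MRI/CRP by default.** SAP 6.1.2.1 says so unless otherwise specified, and 6.15.1 specifies its own model. A main effect alone would not help, because the problem is a difference in treatment effect between strata.

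**Further subgroup analyses are allowed.** They are, in SAP 6.15.1 and Protocol 9.7.2, but nothing in the visible text commits to this one.

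**The inflation is slight at the only documented share.** At 20% it is 0 to 2 percentage points. This stands. Much larger rates can be produced (27% at a 33% MRI-negative share, 42% at 40%), but only by assuming that ixekizumab has no effect at all in MRI-negative patients. The documents give no basis for that.

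**Redaction.** A reader might infer that no planned analysis separates HLA-B27 from MRI. That cannot be asserted: the text of SAP 6.15.3, on subgroup identification, is blacked out.

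**Conclusion.** The concern holds as a structural limitation of an exploratory analysis. The overlap follows from the eligibility criteria alone. Any distortion of the HLA-B27 result depends on the effect differing between MRI/CRP strata. Its size rests on an assumed effect gap, an assumed 70% HLA-B27-positive share and, above 20%, an assumed MRI-negative share.

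Four limits apply:

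- The statement covers eligible patients. Inadvertently enrolled patients may continue (Protocol 7.1.2), and the ITT population keeps everyone randomized.
- MRI-positive means the ASAS/OMERACT screening reading, not the SPARCC cut-off of 2 used for the SAP's baseline MRI subgroup.
- All eligible MRI-negative patients have elevated screening CRP, so the mixing is with the whole MRI/CRP stratum rather than MRI alone.
- The primary and major secondary analyses are unaffected: randomization is stratified by MRI/CRP status, their models adjust for it, and subgroup tests lie outside the multiplicity scheme.

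The point is modest, but the change is cheap.

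**What to change.** In SAP 6.15.1:

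1. Keep the all-patient HLA-B27 table and label it descriptive.
2. Add the HLA-B27 interaction test and within-subgroup comparisons in patients with positive screening MRI. Alternatively, add screening MRI/CRP status and its interaction with treatment to the HLA-B27 model; the main effect alone is not enough.
3. State that eligibility makes HLA-B27-negative patients MRI-positive, and that HLA-B27 cannot be assessed in MRI-negative patients.

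This takes a few sentences and one more table, using data already collected. The restricted comparison loses the MRI-negative patients, about 20 of 100 per arm at a 20% share and 40 of 100 at a 40% share. In simulation, a true 15-point HLA-B27 difference was detected in about 17-21% of trials when restricted, against 22-23% with all patients. For a 25-point difference the figures were 33-40% against 42-43%. Power is low either way, so the restricted result should be read mainly through its estimates and confidence intervals.

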**SpA features:**

- **Inflammatory back pain (IBP):** IBP according to experts: four out of five of the following parameters present: (1) onset before the age of 40 years, (2) insidious onset, (3) improvement with exercise, (4) no improvement with rest, (5) pain at night (with improvement upon getting up).
- **Arthritis:** Past or present active synovitis diagnosed by a doctor.
- **Enthesitis (heel):** Heel enthesitis: past or present spontaneous pain or tenderness at examination at the site of the insertion of the Achilles tendon or plantar fascia at the calcaneus.
- **Uveitis:** Past or present uveitis anterior, confirmed by an ophthalmologist.
- **Dactylitis:** Past or present dactylitis diagnosed by a doctor.
- **Psoriasis:** Past or present psoriasis diagnosed by a doctor
- **Crohn's/Colitis:** Past or present Crohn's disease or ulcerative colitis diagnosed by a doctor
- **Good response to NSAIDs:** At 24 to 48 h after a full dose of NSAID the back pain was not present anymore or much better.  
**Note:** As patients enrolling into the study should have failed 2 NSAIDs or be intolerant to NSAIDs, a doctor should assess whether patients had "good" prior response to NSAIDs.
- **Family history for SpA:** Presence in first-degree or second-degree relatives of any of the following: (a) ankylosing spondylitis, (b) psoriasis, (c) uveitis, (d) reactive arthritis, (e) IBD.  
**Note:** A doctor should confirm with his/her patient there was a clear diagnosis (not self-diagnosis) for any of these in first- or second-degree relatives.
- **HLA-B27:** positive testing according to standard laboratory techniques
- **Elevated CRP:** CRP >5.00 mg/L in the presence of back pain, after exclusion of other causes for elevated CRP concentration

**References:** Rudwaleit et al. 2009d; Sieper et al. 2009; Aydin et al. 2012.

---

**Appendix 6. Protocol Amendment I1F-MC-RHBX(b)  
Summary: A 52-Week Multicenter, Randomized, Double-  
Blind, Placebo-Controlled Study to Evaluate the Efficacy  
and Safety of Ixekizumab (LY2439821) in bDMARD-Naive  
Patients with Nonradiographic Axial Spondyloarthritis**

---

Protocol I1F-MC-RHBX, A 52-Week Multicenter, Randomized, Double-Blind, Placebo-Controlled Study to Evaluate the Efficacy and Safety of Ixekizumab (LY2439821) in bDMARD-Naive Patients with Nonradiographic Axial Spondyloarthritis, has been amended. The new protocol is indicated by amendment (b) and will be used to conduct the study in place of any preceding version of the protocol.

The overall changes and rationale for the changes made to this protocol are as follows:

- There are now two primary objectives to accommodate regional regulatory requirements.
- Proportion of patients achieving ASAS40 response at Week 52 is removed from the secondary objective and added as a primary objective. Power estimations were added for this objective.
- Clarified that we will use screening MRI/CRP status and not baseline.

Other minor typographical corrections and clarifications not affecting content have been made in the document.

## Revised Protocol Sections

**Note:** Deletions have been identified by ~~strikethroughs~~.  
 Additions have been identified by the use of underscores.

### Section 1. Protocol Synopsis

**Objective(s)/Endpoints:**

There are 2 primary objectives in this study to accommodate regional regulatory requirements.

| Objectives  | Endpoints   |
|---|---|
| 
Primary
                     The primary objective is to compare both ixekizumab regimens (80 mg every 2 weeks [Q2W] or 80 mg every 4 weeks [Q4W]) versus placebo in patients with active nonradiographic axial spondyloarthritis (nonrad-axSpA) <del>at Week 16.</del>
 | 
 
• Proportion of patients achieving an Assessment of Spondyloarthritis International Society 40 (ASAS40) response at Week 16 (for regulatory agencies that accept Week 16 as primary endpoint)
 
• Proportion of patients achieving an ASAS40 response at Week 52 (for regulatory agencies that require Week 52 as primary endpoint)
 
   |
| 
Secondary
 The major secondary objective is:
 
 
• To compare both ixekizumab regimens (80 mg Q2W or 80 mg Q4W) versus placebo in patients with active nonrad-axSpA at Week 16 and Week 52
 
                  | 
 
<del>• Proportion of patients achieving an ASAS40 response at Week 52</del>
 
• Change from baseline in Ankylosing Spondylitis Disease Activity Score (ASDAS) at Week 16
 
• Change from baseline in ASDAS at Week 52
 
• Change from baseline in Bath Ankylosing Spondylitis Functional Index (BASFI) at Week 16
 
• Change from baseline in BASFI at Week 52
 
• Proportion of patients achieving ASDAS inactive disease at Week 16
 
• Proportion of patients achieving ASDAS inactive disease at Week 52
 
• Change from baseline in magnetic resonance imaging (MRI) of the sacroiliac joints (SIJ) (Spondyloarthritis Research Consortium of Canada [SPARCC] score) at Week 16
 
• Percent of patients without clinically meaningful changes in background therapy at Week 52
 
 |

